5.3 Treatment assignment and randomization

Eligible patients will be randomized in a 1:1 ratio to either the active ofatumumab 20 mg group or to the active teriflunomide 14 mg group. The randomization will be stratified by geographical region and by MS subtype (RRMS, SPMS). Study sites can only participate in one of the 2 studies to ensure independence of each study.

On Day 1 (randomization visit), all eligible patients will be randomized via Interactive Response Technology (IRT) to one of the treatment arms. The Investigator or his/her delegate will contact the IRT after confirming that the patient fulfills all the inclusion/exclusion criteria. The IRT will assign a randomization number to the patient, which will be used to link the patient to a treatment arm and will specify a unique medication number for the first package of investigational treatment to be dispensed to the patient. The randomization number will not be communicated to the caller.

The randomization numbers will be generated using the following procedure to ensure that treatment assignment is unbiased and concealed from patients and Investigator staff. A patient randomization list will be produced by the IRT provider using a validated system that automates the random assignment of patient numbers to randomization numbers. These randomization numbers are linked to the different treatment arms, which in turn are linked to medication numbers. A separate medication list will be produced by or under the responsibility of Novartis Drug Supply Management using a validated system that automates the random assignment of medication numbers to packs containing the investigational drug(s).

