9.4.1 Statistical model, hypothesis, and method of analysis

The null hypothesis is that there is no difference in the ARR between ofatumumab 20 mg sc once monthly and teriflunomide 14 mg po once daily in reducing the frequency of confirmed MS relapses as measured by ARR. The alternative hypothesis is that there is a difference between the 2 treatment groups.

- Superiority of ofatumumab 20 mg sc over teriflunomide 14 mg po will be concluded if the observed ARR on ofatumumab 20 mg sc is lower than on teriflunomide 14 mg po and if the null hypothesis can be rejected at the two-sided significance level of 0.05.

[figure not shown]
The null hypothesis will be tested based on the FAS, using a negative binomial regression model with log-link, treatment and region as factors, number of relapses in previous year, baseline EDSS, baseline number of Gd-enhancing lesions and the patient's age at baseline as covariates. In the analysis, the response variable is the number of confirmed relapses observed from each patient and the patient's time in study (natural log of time in years) is used as an offset variable to adjust for the varying lengths of patient's time in the study. The adjusted ARR (i.e., model-based estimate adjusted for covariates) for each treatment and the corresponding 95% confidence interval, and ARR ratio (also expressed as percentage reduction relative to control group) along with the 95% confidence interval for the ARR ratio and the corresponding p-value will be obtained.

The definition of Region is intended to correspond to that used for the stratification of the randomization. However, the definition of Region may be modified and defined in the statistical analysis plan if that is indicated based on statistical criteria (e.g. non-convergence of models). In addition, the statistical analysis plan may define a process how the primary model can be simplified (e.g. by excluding covariates) in case of non-convergence.

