2.5.2 Statistical hypothesis, model, and method of analysis

The null hypothesis is that there is no difference in the ARR between ofatumumab 20mg sc once monthly and teriflunomide 14 mg po once daily in reducing the frequency of confirmed MS relapses as measured by ARR. The alternative hypothesis is that there is a difference between the two treatment groups.

Superiority of ofatumumab 20mg sc over teriflunomide 14 mg po will be concluded if the observed ARR on ofatumumab 20mg sc is lower than on teriflunomide 14 mg po and if the null hypothesis can be rejected at the two-sided significance level of 0.05.

The null hypothesis will be tested based on the FAS, using a negative binomial regression model with log-link, treatment and region as factors, number of relapses in previous year, baseline

[figure not shown]
EDSS, baseline number of T1 Gd-enhancing lesions and the patient's age at baseline as covariates. In the analysis, the response variable is the number of confirmed relapses observed from each patient and the patient's time in study (natural log of time in years) is used as an offset variable to adjust for the varying lengths of patient's time in the study. The adjusted ARR (i.e., model-based estimate adjusted for covariates) for each treatment and the corresponding 95% confidence interval, and ARR ratio (also expressed as percentage reduction relative to control group) along with the 95% confidence interval for the ARR ratio and the corresponding p-value will be obtained.

The definition of Region is intended to correspond to that used for the stratification of the randomization. However, the definition of Region may be modified if that is indicated based on statistical criteria (e.g. non-convergence of models).

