2.6.2 Statistical hypothesis, model, and method of analysis

2.6.2.1 Disability worsening (3-month or 6-month confirmed)

Hypothesis and Analysis of disability worsening (3mCDW, 6mCDW)

The hypothesis and the analysis methods will be identical for 3mCDW and 6mCDW. For brevity the hypothesis and analysis methods are only specified in full for 3mCDW.

The null hypothesis is that there is no difference in the time to 3mCDW between ofatumumab 20mg sc and teriflunomide 14 mg po

- Superiority of ofatumumab 20mg sc over teriflunomide 14 mg po will be concluded if there is a reduction in risk (estimated hazard ratio from Cox-model <1) in patients treated with ofatumumab compared with teriflunomide and the observed p-value for the between-treatment comparison is less than the two-sided significance level of 0.04875 ($=2*[0.025-0.025^2]$). The multiplicity adjustment explained in [Section 2.5.3](#) applies.

Confirmatory analysis for disability-related endpoints: The confirmatory analysis of time to 3mCDW will be done in a meta-analysis based on the combined FAS populations from G2301 and G2302.

The null hypothesis will be tested using a stratified Cox proportional hazards model with study as stratum, treatment, and region as factors and baseline EDSS as a continuous covariate. For confirmatory purposes the hazard ratio between ofatumumab and teriflunomide will be estimated with 95% confidence interval and p-value from the combined data from both studies in this meta-analysis. In addition, an expanded model with a treatment-by-study interaction will be fit to the data and between-study heterogeneity will be tested as the type-3 test of the treatment-by-study interaction; the corresponding p-value will be provided. For information only, the hazard ratio for each study will be estimated by study from the same expanded model with corresponding 95% confidence intervals and p-values.

Supportive analysis: The confirmatory analysis of time to 3mCDW will also be done in a meta-analysis based on the combined per-protocol sets from G2301 and G2302.

Kaplan-Meier curves (and/or cumulative incidence plots) will be provided by treatment for the combined study populations to present the time-dependent cumulative probability of patients reaching 3mCDW. Kaplan-Meier curves (and/or cumulative incidence plots) and KM estimates by treatment will also be provided by study.

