2.6.2.3 Number of Gd-enhancing lesions per scan

The null hypothesis is that there is no difference in the number of Gd-lesion per scan between ofatumumab 20mg sc and teriflunomide 14 mg po

- Superiority of ofatumumab 20mg sc over teriflunomide 14 mg po will be concluded if there are fewer Gd-lesions per scan (estimated rate ratio from a negative binomial model < 1) in patients treated with ofatumumab compared with teriflunomide and the observed p-value for the between-treatment comparison is less than the two-sided significance level of 0.05. The multiplicity adjustment explained in [Section 2.5.3](#) applies.

Confirmatory analysis of the number of Gd-lesions per scan: The confirmatory analysis of the number of Gd-lesions per MRI-scan will be done based on the FAS using a negative binomial regression model with log-link. The total number of Gd-enhancing T1 lesions (derived as in [Section 2.6.1.3](#)) will be used as the response variable, and the natural log of the number of MRI-scans (derived as in [Section 2.6.1.3](#)) will serve as the offset variable to adjust for the different number of MRI-scans between patients related to the flexible follow-up time in this study. The model will include treatment and region (factors), and age, and number of Gd-enhancing T1 lesions at baseline as continuous covariates.

The number of Gd-lesions per scan will be estimated by treatment with 95% confidence interval. The between treatment effect will be calculated as rate-ratio with 95% confidence interval and p-value. In addition the relative reduction in the number of Gd-lesion per scan will be computed as one (1) minus the rate-ratio and expressed as a percentage.

Supportive analysis: The number of Gd-lesions will be summarized descriptively by visit-window and treatment group.

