2.6.2.4 Annualized rate of new or enlarging T2 lesions

The null hypothesis is that there is no difference in the number of new or enlarging T2 lesions between ofatumumab 20mg sc and teriflunomide 14 mg po

- Superiority of ofatumumab 20mg sc over teriflunomide 14 mg po will be concluded if there are fewer new or enlarging T2 lesions (estimated rate ratio from a negative binomial model < 1) in patients treated with ofatumumab compared with teriflunomide and the observed p-value for the between-treatment comparison is less than the two-sided significance level of 0.05. The multiplicity adjustment explained in [Section 2.5.3](#) applies.

Confirmatory analysis of the Annualized rate of new or enlarging T2 lesions: The confirmatory analysis of the annualized rate of new or enlarging T2 lesions will be done based on the FAS using a negative binomial regression model with log-link. The number of new or enlarging T2 lesions on the last available MRI scan relative to baseline (derived as in [Section](#)

[2.6.1.4](#)) will be used as the response variable, and the natural log of the time (in years) of the MRI assessment from the baseline scan (as defined in [Section 2.6.1.4](#)) will serve as the offset variable to adjust for the various lengths of follow-up times between patients in this study. The model will include treatment and region (factors), and age, and baseline volume of T2 lesions as continuous covariates.

The number of new or enlarging T2 lesions per year will be estimated by treatment with 95% confidence interval. The between treatment effect will be calculated as rate-ratio with 95% confidence interval and p-value. In addition the relative reduction in the number new or enlarging T2 lesions per year will be computed as one (1) minus the rate-ratio and expressed as a percentage.

Supportive analysis: The number of new or enlarging T2 lesions collected at each visit will be summarized descriptively by treatment group.

The number of new or enlarging T2 lesions are a cumulative measure of disease activity. Since the number of new or enlarging T2 lesion is assessed relative to the MRI scan collected at screening (i.e. well before the start of study medication intake), it is expected that this analysis underestimates the true treatment effect. Therefore, a supportive analysis will be performed based on the new or enlarging T2 lesions between the Month 12 scan and the End of Study scan.

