2.6.2.5 Neurofilament light chain (NfL)

The null hypothesis is that there is no difference in NfL between ofatumumab 20 mg sc and teriflunomide 14 mg po by month 3.

- Superiority of ofatumumab 20 mg sc over teriflunomide 14 mg po will be concluded if NfL levels are already lower at month 3 in patients treated with ofatumumab compared with teriflunomide and the observed p-value for the between-treatment comparison is less than the two-sided significance level of 0.05. The multiplicity adjustment explained in [Section 2.5.3](#) applies.
- **Confirmatory analysis of NfL:** The NfL concentration (geometric mean concentration) will be estimated by treatment and time point with 95% confidence intervals using a repeated measures model on the basis of all evaluable log-transformed NfL values (the natural log will be used). The response variable is the log-transformed values of the NfL level as the NfL level is expected to follow log-normal distribution. The exponentiated treatment differences are the geometric mean ratios (GMR) which will be reported by visit window with 95% confidence intervals and p-values. The statistical hypothesis test will be based on the treatment contrast and p-value obtained at month 3. An unstructured covariance matrix will be used. The model will include treatment, region and visit window as factors, and age, number of Gd-enhancing lesions at baseline, baseline T2 lesion volume and the log-transformed NfL baseline concentration as continuous adjustments. The model will also include a treatment-by-timepoint interaction to allow the treatment effect to vary over time. The treatment effect of ofatumumab versus teriflunomide will be visualized in a line plot with 95% confidence intervals.

Supportive analysis: If ofatumumab significantly reduces NfL as compared with teriflunomide, the following additional analyses will be performed. In all patients (FAS), and additionally in the subgroup of newly diagnosed (within 3 years prior to the screening visit) and treatment-

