2.6.2.6 Brain volume loss

The null hypothesis is that there is no difference in brain volume change between ofatumumab 20mg sc and teriflunomide 14 mg po

- Superiority of ofatumumab 20mg sc over teriflunomide 14 mg po will be concluded if there is less brain volume loss (positive difference in slope from the random coefficient model) in patients treated with ofatumumab compared with teriflunomide and the observed p-value for the between-treatment comparison is less than the two-sided significance level of 0.05. The multiplicity adjustment explained in [Section 2.5.3](#) applies.

Confirmatory analysis of brain volume loss: The percentage change from baseline in brain volume will be estimated on the basis of all scheduled scans up to the last available MRI scan that evaluated percentage brain volume change relative to baseline. A random coefficients model will be used as main analysis for this endpoint in order to adjust for the various length of follow-up time in this study. Brain volume change was approximately linear over time and approximately normally distributed in 3 independent studies of the fingolimod phase 3 program. The random coefficients model will include treatment, region as fixed effects (factors), and time, number of Gd-enhancing lesions at baseline, baseline T2 volume, and normalized brain volume at baseline as continuous covariates and treatment by time interaction. Time as a continuous covariate allows for estimation of different slopes and intercepts among treatment groups. The model will also contain random terms to account for deviations about the population slope and intercept. The statistical test will address the question whether there is a difference in the slope of brain volume change by treatment group. The annual rate of percent change from baseline in brain volume is approximates as the population slope within the treatment group. Since the random coefficients model allows for the estimation of different slopes and intercepts among the treatment groups, differences between treatments at any time can be summarized using this model. Model estimates of percentage brain volume change at Months 12 and 24 will be provided by treatment with corresponding 95% confidence interval. Treatment differences will be estimated at the same time points with confidence interval and a p-value for the test of a difference in slope.

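### Randomisation is stratified by region and MS subtype, but none of the eight confirmatory models includes subtype and no reason is given; on stated assumptions the forgone power is under one point.

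*Protocol*

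**What the plan says.** Protocol 5.3 and SAP 1.1 both name two randomisation strata: "The randomization will be stratified by geographical region and by MS subtype (RRMS, SPMS").

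The confirmatory models keep the first stratum and not the second:

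- **ARR.** Protocol 9.4.1: "using a negative binomial regression model with log-link, treatment and region as factors". SAP 2.5.2 has the same model, "using a negative binomial regression model with log-link, treatment and region as factors, number of relapses in previous year", followed by baseline EDSS, Gd lesion count and age.
- **3mCDW, 6mCDW, 6mCDI** (SAP 2.6.2.1 and 2.6.2.2): "stratified Cox proportional hazards model with study as stratum, treatment, and region as factors and baseline EDSS as a continuous covariate".
- **Gd lesions** (SAP 2.6.2.3): "treatment and region (factors), and age, and number of Gd-enhancing T1 lesions at baseline as continuous covariates".
- **T2 lesions** (SAP 2.6.2.4): "model will include treatment and region (factors), and age, and baseline volume of T2 lesions as continuous covariates".
- **NfL** (SAP 2.6.2.5): "The model will include treatment, region and visit window as factors, and age, number of Gd-enhancing lesions at baseline", with T2 volume and baseline log NfL.
- **Brain volume** (SAP 2.6.2.6): "The random coefficients model will include treatment, region as fixed effects (factors), and time, number of Gd-enhancing lesions at baseline", with T2 volume and normalised brain volume.

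Protocol 9.4.1 and SAP 2.1 tie the region term to the randomisation strata. Nothing similar is said for subtype. Subtype appears in the baseline description (SAP 2.3.3). It is absent from the efficacy subgroups (SAP 2.2.1) and from the list of changes to protocol analyses (SAP 4).

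**The concern.** A factor is normally chosen for stratification because it is expected to matter for outcome, and an analysis that reflects the randomisation would then carry it. Protocol 1.1 itself describes SPMS as a stage in which disability worsens independently of relapses, so subtype could well be prognostic for the disability endpoints. The Cox models for those endpoints adjust only for region and baseline EDSS, which leaves little else to stand in for it.

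Stratifying by a prognostic factor and then leaving it out makes the reported standard error slightly too large for the balance that the design achieved. At stake are some precision at almost no cost, and a question that a reader of the results will ask: do the findings hold when the analysis reflects both strata?

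**Working it through.** **Assumptions.** The documents give neither the SPMS share p nor its effect. I take p = 5-20%, a rate or hazard ratio of 0.5 or 2, and a brain volume difference of 0.25-0.5 SD. Planned evaluable size is 900 × 0.8 = 720, or 360 per arm (Protocol 9.8 and 9.8.1).

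**ARR: the plan's own figure.** Inputs are rates 0.168 and 0.28, T = 1.5 years and κ = 0.82 (Protocol 9.7.2.3). The expected counts are 0.252 and 0.42.

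- At 322 per arm, I = 322 / (1/0.252 + 1/0.42 + 2 × 0.82) = 322 / 7.989 = 40.30. Power = Φ(0.5108 × √40.30 − 1.96) = 90.0%, as stated.
- At 360 per arm, I = 45.06 and power is 92.9%.

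**ARR: omitted against adjusted.** Let r be the rate in a subtype relative to the overall mean and E2 the mean of r². Take 0.82 as the dispersion over both subtypes together.

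- Dispersion within subtype: κ_adj = 1.82/E2 − 1.
- Subtype omitted: the model reports I_rep = 45.06. With subtype balanced by design, the information is really I_act = 360 / (3.968 + 2.381 + 2(1.82 − E2)). Power = Φ((0.5108 − 1.96/√I_rep) × √I_act).
- Subtype included: I_adj is the sum over subtypes of n_s / (1/(0.252 r_s) + 1/(0.42 r_s) + 2κ_adj). Power = Φ(0.5108 × √I_adj − 1.96).

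Example, 20% share and rate ratio 2: r = 1.667 and 0.833, E2 = 1.111, κ_adj = 0.638, I_act = 360/7.767 = 46.35, I_adj = 46.54.

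| Share, rate ratio | I_act | I_adj | Omitted | Adjusted | Gain (points) |
|---|---|---|---|---|---|
| 5%, 0.5 | 45.20 | 45.22 | 92.94% | 92.99% | 0.05 |
| 20%, 0.5 | 45.62 | 45.68 | 93.03% | 93.22% | 0.19 |
| 5%, 2 | 45.55 | 45.66 | 93.02% | 93.21% | 0.20 |
| 20%, 2 | 46.35 | 46.54 | 93.19% | 93.63% | 0.45 |
| 20%, 3 | 49.07 | 49.32 | 93.74% | 94.82% | 1.08 |

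Gains are taken before rounding. At 322 per arm the same formulas give 0.06-0.58 for the twofold cases and 1.43 for a threefold ratio at 20%. Simulation at 322 per arm (4,000 runs per case, twofold ratios) gave gains of 0.0-0.6 points. Two-sided type I error was 4.75-5.05% with subtype omitted and 4.73-5.25% with it included.

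**Brain volume.** Protocol 9.8.8 gives a 25% reduction from 0.45%, that is 0.1125, and SD 0.5%. At n = 621, e = 0.1125 / (0.5 × 2/√621) = 2.80 and power is 80.1%, as stated. At n = 720, e = 3.02 and power is 85.5%. With R² = p(1 − p)d², omitted power is Φ((e − 1.96)/√(1 − R²)) and adjusted power is Φ(e/√(1 − R²) − 1.96).

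| Share, SD difference | R² | Omitted | Adjusted | Gain (points) | Type I error, omitted |
|---|---|---|---|---|---|
| 5%, 0.25 | 0.003 | 85.55% | 85.62% | 0.07 | 4.97% |
| 5%, 0.5 | 0.012 | 85.66% | 85.92% | 0.26 | 4.86% |
| 20%, 0.25 | 0.010 | 85.63% | 85.86% | 0.22 | 4.89% |
| 20%, 0.5 | 0.040 | 86.01% | 86.89% | 0.88 | 4.55% |

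**3mCDW.** The Schoenfeld formula, 4(z + z)²/ln(0.614)² with one-sided α 0.024375, gives 178 events at 90% power and 133 at 80%, both as stated. Simulation used 1,800 patients, about 175 events, follow-up assumed uniform over 1-2.5 years, and 8,000 runs per case. The standard error was about 0.156 with or without subtype, and the gain 0.0-0.3 points. Type I error at 4.875% was 4.5-4.9% omitted and 4.6-5.0% adjusted. An analytic approximation is a little higher at a 20% share and hazard ratio 2: 0.38 points for 3mCDW and 0.42 for 6mCDW. 6mCDI was not computed separately.

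**Gd, T2, NfL.** At 360 per arm, planned power is already above 99.9% for each, so there is nothing material to gain.

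**The case against.** The strongest reply is that this is a covariate preference with trivial consequence. The models are prespecified, their tests keep their level, and relapse history, EDSS, age, lesion load or brain volume may already carry part of any subtype effect. The calculations give subtype its full unadjusted effect, so they lean towards the largest gain. Sparse SPMS numbers are a plausible reason for the omission. All of that stands, and it limits the point to a minor one. It does not supply the missing reason: the documents deal openly with small regions by merging them (SAP 2.1) and are silent on subtype.

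A reader might infer that ARR power falls below its target. If 0.82 were the dispersion within subtype, a 20% share and a rate ratio of 2 would raise the overall value to 1.82 × 1.111 − 1 = 1.022 and give 88.6% power at 322 per arm, about a point below the adjusted model. The documents do not support that reading. Protocol 9.7.2.2 and 9.7.2.3 hold each study open until it has 40.3 units of information, with dispersion re-estimated from pooled blinded data. Extra heterogeneity would therefore lengthen follow-up, within the 30-month maximum, rather than leave power short. The comparison also uses the minimum size rather than the planned one, and ignores the balance from stratification.

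**Conclusion.** The mismatch is real: two strata, eight confirmatory models, one stratum in all of them and the other in none, without explanation. It is not an error in any stated figure, and the omission does not inflate type I error.

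Under the assumptions set out above, the forgone power at the planned size is about 0.05-0.45 points for ARR, 0.07-0.9 for brain volume and 0-0.3 for 3mCDW (about 0.4 by the approximation), and negligible for Gd, T2 and NfL. These figures describe assumed inputs, not this trial's population. A threefold rate difference would give about 1 point or slightly more for ARR; covariates already in the models would pull all the figures down.

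It would also be too strong to say that the plan breaks a commitment to adjust for both strata. The documents make that link for region only.

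**What to change.** **Before database lock:** add MS subtype as randomised (the IRT value) as a factor in the ARR, Gd, T2, NfL and brain volume models and in the Cox models for 3mCDW, 6mCDW and 6mCDI. Drop it only for non-convergence, under a rule fixed before unblinding. The cost is one degree of freedom per model and a sentence or two of SAP text.

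**For the version already past lock** (the SAP history has an October 2019 addendum dated after it): keep the confirmatory models as written. Report subtype-adjusted versions as labelled sensitivity analyses, and state in one sentence why subtype was left out. The cost is one extra analysis per endpoint.
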